### 540 **4.1 Primary Hypothesis:**

- 541 1) Relative to infants receiving whole body cooling for 72 hours, cooling for 120  
542 hours will reduce death or disability
- 543 2) Relative to infants receiving whole body cooling at an esophageal temperature of  
544 33.5°C, cooling to an esophageal temperature of 32.0°C will decrease death or  
545 disability

546 **4.2 Secondary Hypotheses:**

- 547 1) There will be no statistical interaction between the two factors tested in this trial  
548 2) Cooling to a greater depth and/or longer duration will result in the following:  
549 a. No increase in acute adverse events among infants cooled for 120 hours  
550 b. No increase in acute adverse events among infants cooled to 32.0°C  
551 c. Mean Cognitive score at 18-22 months of age will be higher among infants cooled  
552 for 120 hours  
553 d. Mean Cognitive score at 18-22 months will be higher among infants cooled to  
554 32.0°C  
555

556 A factorial design has been selected because the conditions are ideal for such an approach  
557 (Piantadosi 05). Namely, the interventions can be administered together without  
558 significantly changing the intensity/magnitude of each in the presence of the other. In  
559 addition, there is interest in learning about the effect of the two combined interventions  
560 on outcome, and large statistical interactions between the 2 treatments (longer cooling,  
561 deeper cooling) are not anticipated. The mechanisms of neuroprotection associated with  
562 longer or deeper cooling are likely to be similar to mechanisms associated with  
563 neuroprotection using shorter or lesser degrees of hypothermia but may differ in the  
564 extent of mechanisms involved.  
565

566 Since safety and feasibility of cooling infants with HIE to the duration and depth  
567 proposed in this study has not been performed to date, the Data Safety Monitoring  
568 Committee (DSMC) of the NRN will examine data after the first 40 subjects (10 in each  
569 arm of the factorial design) are randomized into the proposed study. Enrolment will be  
570 temporarily halted while the DSMC reviews the first interim analysis for safety and will  
571 be resumed after the DSMC, on review of this data, decides that recruitment may  
572 commence. This approach is similar to the first RCT of whole body hypothermia  
573 performed by the NRN in 1998 where 20 infants were cooled to 34.5°C vs. control with  

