## 787 **5. STATISTICAL CONSIDERATIONS**

788

789 **5.1 Sample Size:** Sample size calculations for this 2x 2 factorial design assume that there  
790 are no large statistical interactions between the 2 factors being tested --- longer and  
791 deeper cooling. Note that this does not preclude us from testing for the presence of such  
792 an interaction (indeed, it figures as the first secondary hypotheses presented earlier), but  
793 that we are not powering the trial to detect such an interaction.

794

795 In a 2 by 2 factorial design we are essentially superimposing one trial on another -- in this  
796 case, a trial of longer vs. usual duration of cooling, and a trial of deeper vs. usual depth of  
797 cooling. So, unless we want to power for a statistical interaction (which we are not doing  
798 here), we power such a trial for a comparison between the 2 groups ("outside the table",  
799 or marginal analysis) -- longer vs. usual duration of cooling (regardless of depth of  
800 cooling), i.e., groups X vs. Y in Fig. 2 or deeper vs. usual depth of cooling (regardless of  
801 duration of cooling), i.e., groups A vs. B in Fig. 2.

802

803 The following event rates in the 4 cells of the factorial trial design are assumed:  
804 AX=45%, AY=BX=30%, BY=25%. An event rate of 45% for the control group (standard  
805 duration of cooling for 72 hours and standard depth of cooling to 33.5°C) is assumed  
806 based on the primary outcome of the NICHD RCT of whole body hypothermia for HIE  
807 ([name] 05). An event rate of 30% in AY and BX is an estimate. We acknowledge the  
808 event rates will depend on proportion of infants with moderate and severe HIE. We  
809 assume that BY (with the longer and deeper cooling combined) would have the lowest  
810 event rate of 25%. However, we are aware that this group may also be at highest risk for

811 complications of longer and deeper cooling. Assuming that we are principally interested  
812 only in testing the marginal effects of A vs. B or X vs. Y (which translates into a  
813 comparison of event rates of 37.5% vs. 27.5%), a sample size of 363 per group (A or B,  
814 or X or Y), for a total of 726, is needed with a two-tailed test, with Type I error set at 5%,  
815 power set at 80%, and allowing for 5% loss to follow up.

816

817 Two approaches will be used to monitor duration of the trial. Sites will be encouraged to  

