848 objective to test for statistical interactions.

849

850 The data in the two groups in the factorial design will be analyzed for treatment group  
851 differences with Chi square or Fisher’s exact tests for the categorical variables and with t-  
852 tests for the continuous variables. The primary and secondary outcomes will be analyzed  
853 using robust Poisson regression models (for binary outcomes) to generate risk ratios  
854 adjusting for the stratification variables (level of HIE and site). The NICHD NRN DSMC  
855 will monitor progress of the study for safety at pre-specified time points. The DSMC will

856  
857  
858  
859  
860  
861  
862  
863  
864

be required to evaluate safety of greater depth and longer duration of cooling after the every 25 infants have been enrolled in the trial.

The Bayesian analyses for different scenarios are note below:

Factorial design with total of 726 subjects (363 per group, A or B, or X or Y) comparing event rates of 37.5% vs. 27.5%

	Posterior Probability of Benefit					
	>0% reduction in death or impairment		>10% reduction in death or impairment		>20% reduction in death or impairment	
	Prior	Posterior	Prior	Posterior	Prior	Posterior
Perspective						
Neutral	.50	.997	.37	.96	.25	.72
Skeptical	.30	.99	.21	.94	.13	.67

865  
866  
867  
868  
869

Factorial design with a total of 726 subjects (363 per group) comparing event rates of 35% vs. 30%

	Posterior Probability of Benefit					
	>0% reduction in death or impairment		>10% reduction in death or impairment		>20% reduction in death or impairment	
	Prior	Posterior	Prior	Posterior	Prior	Posterior
Perspective						
Neutral	.50	.92	.37	.64	.26	.21
Skeptical	.30	.89	.21	.58	.13	.17

870  
871  
872  
873  
874

Factorial design with total of 516 subjects (258 per group, A or B or X or Y) comparing event rates of 37.5% vs. 27.5%

	Posterior Probability of Benefit					
	>0% reduction in death or impairment		>10% reduction in death or impairment		>20% reduction in death or impairment	
	Prior	Posterior	Prior	Posterior	Prior	Posterior
Perspective						
Neutral	.50	.99	.37	.92	.26	.66
Skeptical	.30	.98	.21	.89	.13	.60

875  
876  
877  
878  
879

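### The cognitive-score hypotheses rest on unadjusted t-tests among survivors: use a stratum-adjusted linear model labelled as conditional on survival (minor)

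*Protocol*

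**What the plan says.** - Section 4.2 states two hypotheses on the mean score: "c. Mean Cognitive score at 18-22 months of age will be higher among infants cooled" for 120 hours, and "d. Mean Cognitive score at 18-22 months will be higher among infants cooled to" 32.0°C.
- Section 5.2 assigns chi-square or Fisher's exact tests to categorical variables and t-tests to continuous ones: "tests for the continuous variables. The primary and secondary outcomes will be analyzed" "using robust Poisson regression models (for binary outcomes) to generate risk ratios". That regression is adjusted for level of HIE and site. No model is named for a continuous outcome.
- Section 4.5 stratifies randomization by clinical site and stage of encephalopathy.
- Section 4.13 follows surviving infants to 18-22 months. No rule gives a dead infant a score or a rank.
- Section 5.2 also describes every analysis as intention-to-treat.
- Appendix B budgets follow-up on 75% survival. Table 2 in section 3.1 shows 23 deaths among 101 cooled infants in the earlier trial.

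**The concern.** The protocol treats its two kinds of outcome differently for no stated reason. Binary outcomes are adjusted for the variables used to stratify randomization; continuous outcomes are not. After stratified randomization, a plain t-test leaves prognostic between-stratum variation in its error term, so its standard error is too large.

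The second issue is who enters the comparison. A mean score exists only for infants alive at follow-up, so the two groups are defined partly by an event after randomization. If one regimen saves very sick infants, their low scores pull its survivor mean down. If it costs lives among the sickest, its survivor mean rises and 2c or 2d may look supported. A mortality difference is not far-fetched here. The design targets a 10-point fall in death or disability, and in Table 2, 23 of the 44 primary events were deaths. If that share held (an assumption), about 10 × 23/44 = 5.2 of the 10 points would be deaths.

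**Working it through.** **1. The plan's own figure.** Section 5.1 gives: "comparison of event rates of 37.5% vs. 27.5%), a sample size of 363 per group (A or B", "or X or Y), for a total of 726, is needed with a two-tailed test, with Type I error set at 5"%, "power set at 80%, and allowing for 5% loss to follow up". The pooled-variance formula without continuity correction gives 344 per group, and 344/0.95 = 362.1, rounded up to 363 per group and 726 in total. This reproduces. The protocol gives no power for the cognitive score.

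**2. Infants with a score.** 363 × 0.75 × 0.95 ≈ 259 per margin, so (363 − 259)/363 ≈ 29% of randomized infants are outside the t-test, mostly through death.

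**3. Detectable difference.** (1.96 + 0.84) × √(2/259) ≈ 0.25 SD. That is about 3.7 points if the SD is 15 and 4.9 if it is 20 (SDs assumed; the protocol gives none).

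**4. Precision.** Let p be the severe fraction among scored infants and g the mean score gap between stages. Then R² = p(1−p)g² / [p(1−p)g² + SD²], and the t-test's standard error is too large by a factor 1/√(1−R²). The protocol does not give these inputs for survivors, so ranges are assumed: p 0.20-0.33, g 5-15 points, SD 15-20.

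| p | g | SD | R² | SE factor | actual size of a 5% test |
|---|---|---|---|---|---|
| 0.20 | 5 | 20 | 4/404 = 0.010 | 1.005 | 0.049 |
| 0.25 | 10 | 15 | 18.75/243.75 = 0.077 | 1.041 | 0.041 |
| 0.33 | 15 | 15 | 49.7/274.7 = 0.181 | 1.105 | 0.030 |

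This covers HIE level alone; site would add something unknown.

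**5. Shift from survival, with no effect on cognition.**

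*Latent-normal model.* Death occurs when a standard normal frailty exceeds c = Φ⁻¹(1−m), where m is mortality, and the score is correlated with frailty at strength ρ. The survivor mean is then raised by ρ·φ(c)/(1−m) SD.
- m = 25%: φ(0.674)/0.75 = 0.318/0.75 = 0.424
- m = 30%: φ(0.524)/0.70 = 0.348/0.70 = 0.497
- Difference 0.073 × ρ: 0.029 SD at ρ = 0.4 and 0.044 SD at ρ = 0.6. Dividing by the slightly smaller SD among survivors (about 0.96 and 0.91) gives 0.030 and 0.048 SD.

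Simulations of the same model agree. With mortality 23% against 18% or 28%, ρ 0.4-0.6 and SD 15-20, the shift is 0.4-0.9 points and the 5% t-test rejects about 5-9% of the time. With equal mortality the shift is zero within simulation error. With 23% against 13% it is 0.9-1.8 points and rejection is 11-23%.

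*Worst case.* All extra deaths are the very lowest scorers. The truncated fraction is f = 0.05/0.75 = 6.7%, and the shift is φ(z)/(1−f) = 0.1293/0.9333 = 0.139 SD. For a 2-point mortality difference, f = 2.7% and the shift is 0.06 SD.

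*Check on the scale.* If mortality falls from 25% to 20% and the extra survivors score 10-30 points below the rest, the shift is −(0.05/0.80) × 10 to 30 = −0.6 to −1.9 points (0.04 to 0.125 SD at SD 15). Only an extreme gap comes near the worst case.

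**The case against.** The best defence is that section 5.2 does not decide against adjustment. Its first sentence can be read as simple group comparisons, because binary outcomes appear both there and in the regression sentence. The mention of binary outcomes may only explain the choice of Poisson regression. The protocol nowhere says in words that dead infants are dropped, and an analysis plan not shown here could name a model or a rule for deaths. This lowers the severity, but the point stands: the t-test is the only method given for continuous outcomes, and a test of means with follow-up of survivors leaves the dead out.

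Four stronger readings are tempting and are not supported:
- *That the bias exceeds half the detectable effect.* 0.139/0.25 is indeed over half, but it needs death to sort infants perfectly by a score they would have had at 18-22 months. At correlations of 0.4-0.6 the shift is 12-19% of the detectable effect.
- *That omitting the strata invalidates the test.* It makes the test conservative. The contrast of 32% with 72% by HIE level in section 2.0 is for death or disability; it does not show how strongly HIE level predicts score among survivors.
- *That a rank test with deaths lowest should replace the mean comparison.* Hypotheses 2c and 2d concern mean scores. Such a rank test is another composite of death and function, and it can be positive through survival alone. In the simulations with score unrelated to frailty and mortality 23% against 13%, it rejected 61-64% of the time.
- *That the main result is at risk.* The primary outcome counts deaths and scores below 70 and is stratum-adjusted, and mortality is a listed secondary outcome.

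**Conclusion.** The point holds in a limited form, and its severity is minor. As written, 2c and 2d are tested by a t-test that ignores the randomization strata and compares survivors only, which does not fit the statement that every analysis is intention-to-treat. The standard error is about 0.5-10% too large for HIE level alone, in the conservative direction. The survivor difference could move by about 0.03-0.05 SD for a 5-point mortality difference, with 0.14 SD as the ceiling and nothing if survival is unaffected, against about 0.25 SD detectable. These sizes rest on assumed values for the score SD, the gap by stage, the frailty correlation and the mortality effect, none of which the protocol gives. Only the 75% survival, the 5% loss and the 363 per margin come from it.

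**What to change.** In section 5.2, replace the t-test for cognitive score and the other continuous secondary outcomes (for example Bayley III motor score and growth at follow-up) with a linear model at each margin, adjusted for HIE level, site and the other cooling factor. State that the cognitive-score estimate is conditional on survival and therefore not a comparison of all randomized infants, and report it beside mortality for the same margin. A rank analysis stratified by HIE level and site, with deaths ranked lowest, may be added as a labelled sensitivity analysis; it would use about 363 × 0.95 = 345 infants per margin.

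The cost is a few sentences and a little programming. No extra infants or data are needed, and the sample size of 726 is unchanged. Adjustment does not remove the dependence on survival, which is why the label and the mortality result must go with the estimate.

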### 5.3 Monitoring of Safety for the Trial:

- The protocol will be reviewed by the Institutional Review Board of each participating institution.
- The first interim analysis for safety will be conducted after 40 infants are enrolled (10 in each arm of the factorial design). Enrolment will be temporarily halted while the DSMC reviews the first interim analysis for safety and will be resumed only after the DSMC, on review of this data, is convinced that recruitment may commence.
- Following approval of the DSMC, the temperature data on the infants in the intervention arm of the study will be monitored by the PI and Subcommittee on an ongoing basis to document drops of temperature below target and plans to minimize this complication will be developed. There will be increased vigilance looking for potential complications of a greater depth of hypothermia on cardiac function, increased infection rates, increased bleeding or effects of increased viscosity.
- Serious adverse events will be reported on the MedWatch form to RTI. After the initial interim analysis for safety, serious adverse events will be compared between the treatment groups using sequential analysis methods after every 25 infants have been accrued into the trial. The 2 events that will be monitored include *arrhythmia* requiring therapy (excluding sinus rhythm or mechanical line-placement as a cause) and *major bleeding or thrombosis*. Neonates will be monitored with daily platelet counts and coagulation profile/CBC as clinically indicated. On-going masked central reading of cranial MRI will be undertaken once the MRI secondary study is approved, for evidence of CNS infarct/hemorrhage that is higher than the frequency noted in the NRN study evaluating cranial MRI among infants in the whole body hypothermia for neonatal HIE. The computed statistic will be compared to Pocock boundaries that are constructed beforehand so that an overall alpha level of 5% is maintained. RTI will be responsible for reporting adverse events to the DSMC of the Network.
- All protocol deviations/violations will be monitored by RTI.
- RTI will prepare reports for presentation to the DSMC at periodic intervals.
- DSMC will be responsible for monitoring the safety of the trial. Pre-specified looks will occur at 25%, 50%, 75% and 100% of data accrual at the conclusion of the study intervention.

- Efficacy of the trial with respect to the primary outcome will be monitored during the above specified looks at the data, as feasible, based on recruitment and follow up data accrual.

## 6.0 DURATION OF THE STUDY

The duration of the study is estimated to be 5 years for enrollment and 1.5 years for follow up, with a total of 6.5 years. This projection is based on a survey conducted in June 2009 of all the current NICHD NRN sites to examine study feasibility (see enclosed survey results). To summarize, the number of infants who have undergone whole body hypothermia at < 6 hours of age with eligibility criteria similar to the current proposal is as follows: In 2006, with 11 sites performing cooling for HIE, 108 infants were cooled. In 2007, with 12 sites, this number was 116. In 2008 200 infants were cooled while in 2009 with data from satellite sites (Duke University, Yale University and Wayne State University), 90 infants were cooled between January 1 and May 31 2009.

The consent rate for the first NICHD trial of hypothermia for HIE was 87% (208 of 239 eligible, [name] 05). We anticipate a similar consent rate for the proposed study. The proposed study has estimated a 5% loss to follow up rate; however, it should be noted that the first NICHD NRN trial of hypothermia for HIE had primary outcome data available for 205/208 infants ([name] 05). Therefore, with a high consent rate, we are confident we can enroll 726 subjects prior to 5 years and complete follow up with a high compliance rate in an additional 1.5 years.

## 7.0 CONCLUSIONS

The goal of this protocol is to refine the intervention of whole body hypothermia for neonatal hypoxic-ischemic encephalopathy among term infants by testing both a longer duration of cooling and a greater depth of cooling. We anticipate recruitment into this study will be completed before newer pharmacological therapies (i.e. Erythropoietin) are ready to be in tested in randomized controlled trials following completion of pharmacokinetic, safety and efficacy studies with these agents (Juul 08, Fauchere 08).

The NICHD NRN is uniquely positioned to perform this trial; term infants with neonatal HIE are a non-competing population for research in the Network. A short study start-up time is expected as NRN sites are already trained, and have the equipment, study forms and manual of operations based on prior and on-going hypothermia studies. This study would encourage standard management of cooled infants regardless of randomization group, while optimizing cooling strategies as neuroprotection for neonatal hypoxic-ischemic encephalopathy.

## 8.0. SUGGESTED SECONDARY STUDIES

- 1) Fetal Heart Rate tracings and outcome (central reader for tracings)
- 2) aEEG amplitude and outcome during longer, deeper cooling ([name])
- 3) Impact of sedatives/analgesics/anticonvulsants levels on aEEG background ([name])

- 959 4) Economic analysis of neuroprotection with hypothermia  
960 5) Platelet activation and aggregation with longer, deeper cooling ([name])  
961 6) Biomarkers of brain injury during longer, deeper cooling ([name]/[name])  
962 7) Genetic markers of HIE ([name], [name])  
963 8) Cytokines and longer/deeper cooling in HIE ([name])  
964 9) Hypercoagulable states during longer deeper cooling ([name])  
965 10) Outcome following low Apgar scores ([name])  
966 11) Neonatal MRI as a predictor of outcome with longer, deeper cooling ([name],  
967 [name], [name], [name])  
968 12) The role of hypocarbia in neonatal HIE ([name])  
969 13) Renal dysfunction in neonatal HIE ([name], [name])  
970 14) aEEG during Rewarming ([name], [name], [name], [name], [name], [name])  
971 15) Referral hospital and transport practices for neonates with HIE ([name], [name],  
972 [name])

Appendix A

990	
991	
992	Protocol Versions as Working Drafts
993	2007 October (concept)
994	April 4, 2008
995	August 15, 2008
996	September 18, 2008
997	November 17, 2008
998	June 5, 2009
999	July 15, 2009
1000	October 21, 2009
1001	December 16, 2009
1002	December 22 2009
1003	January 27, 2010
1004	March 23, 2010
1005	April 8, 2010

Appendix B

1006  
1007  
1008  
1009  
1010  
1011

**Budget and Justification:** The following estimated budget is provided for the entire trial assuming enrollment of 726 subjects

	Cost per subject	Number	
Main Study Capitation	1660	726	1,205,160
Follow up	1200	530	636,000
HUS for first 40 patients	200	40	8,000
Training meeting	2000	16	32,000
Equipment and supplies			
Blanketrol	7900	16	126,400
Temperature Probes	60	726	43,560
Total Direct costs			2,051,120
Total Indirect costs@52%	1,881,160	52%	978,203
Total Cost			3,029,323

1012  
1013  
1014  
1015  
1016  
1017  
1018  
1019  
1020  
1021  
1022  
1023  
1024  
1025  
1026  
1027  
1028  
1029  
1030  
1031  
1032  
1033

Research time: Costs will cover time to screen and determine eligibility of patients, data collection, initiating and monitoring of the cooling intervention, and transmission of all data items.

Medical supplies: Costs will cover supplies for the Cincinnati Sub-Zero Blanketrol including Blanketrol equipment, temperature probes, thermal blankets, and temperature probe adaptors.

Follow-up: Costs will cover tracking infants, incentives to participate in Follow-up and performance of follow-up at Network sites, based on survival rate of 75% in first NICHD NRN trial.

Training meeting: The study PI and coordinator from each Network site will be required to attend one training session in conjunction with the Steering Committee prior to initiation of the trial. Funds are required to cover an additional night of lodging/meals assuming this would occur during a NRN Steering Committee meeting.

1034 **Supplement 2: Material for Bayesian Analysis of Optimizing Cooling**  
1035 **Trial**

1036 **Bayesian model and implementation**

1037 A log binomial model with level of encephalopathy and main effects of cooling duration and  
1038 depth and their interaction was used to estimate posterior median of the RRs and 95% credible  
1039 intervals (CrI). The model also included a random center effect and used neutral priors for  
1040 treatment effects centered at RR of 1 (95% prior interval, 0.5-2.0). Weakly informative priors  
1041 were used for all other parameters to exclude large treatment effects and produce conservative  
1042 estimates of treatment effects

1043 The log binomial model used is similar to the one we previously described for  
1044 an interim analysis of the same trial [1]. Let  $y_{ij}$  indicate the primary outcome  
1045 of death or moderate or severe disability for infant  $i$  in center  $j$ . We assume  $y$   
1046 follows a Bernoulli distribution with probability  $p_{ij}$  of observing the primary  
1047 outcome. The full model is specified as:

$$\log(p_{ij}) = \beta_0 + \beta_1 \text{depth}_i + \beta_2 \text{duration}_i + \beta_3 \text{depth}_i \times \text{duration}_i + \beta_4 \text{level of HIE}_i + u_j$$

1048  $u_j \sim \text{Normal}(0, \tau^2),$

1049 where  $u_j$  is the random center effect to account for within center correlation.  
1050 The binary variables depth and duration are coded as 1 for 32.0°C and 120  
1051 hours (experimental interventions) and 0 otherwise; level of HIE is a  
1052 stratifying variable coded as 1 for severe (0 for moderate).

1053 We used Normal(0,1) priors for  $\beta_0$  and  $\beta_4$ . This prior is mildly informative  
1054 since it excludes relative risk effects  $> 7$  ( $< 0.14$ ). For  $\beta_1$  and  $\beta_2$ , we used  
1055 neutral priors in the log RR scale of Normal(0, 0.35), which have a 95% prior  
1056 interval of 0.5–2.0 in the RR scale. For the interaction term  $\beta_3$ , we used a  
1057 Normal(0, 0.14) prior which a priori gives a very small probability of 0.025  
1058 of a qualitative interaction (meaning that the effect of longer cooling on the  
1059 outcome changes direction in the presence or absence of deeper cooling) [2].  
1060 A weakly informative half-Normal(0,1) prior was used for  $\tau$ . We constrained  
1061 all  $p_{ij} < 1$  in the model.

1062 The model was implemented via Markov Chain Monte [name] (MCMC) methods  
1063 in JAGS. We used 4 MCMC chains with 20,000 iterations each after an initial  
1064 burn-in of 20,000 iterations. Trace plots of all parameters were monitored for  
1065 convergence. We additionally calculated the convergence diagnostic of  
1066 Gelman-Rubin for all parameters. All point estimates reported are posterior  
1067 medians.

1068

1069 **References**

1070 1. Pedroza C, Tyson JE, Das A, [name] A, [name] EF, [name] S, et al. Advantages  
1071 of Bayesian monitoring methods in deciding whether and when to stop a clinical  
1072 trial: an example of a neonatal cooling trial. *Trials*. 2016;17:335.

1073 2. Simon R. Bayesian subset analysis: application to studying treatment-by-  
1074 gender interactions. *Stat. Med.* 2002;21:2909–16.

1075

1076

1077

**Summary of the OPTIMIZING COOLING STRATEGIES AT < 6 HOURS OF AGE FOR NEONATAL HYPOXIC-ISCHEMIC ENCEPHALOPATHY (HIE) Protocol changes**

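### Supplement 2 gives 0.025 as the prior probability of a qualitative interaction; the priors written beside it give about 0.12, and the interaction prior is more informative than the text says.

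*Protocol*

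**What the plan says.** The Bayesian model in Supplement 2 is a log binomial regression on depth, duration, their product, level of encephalopathy and a random centre effect.

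- Main effects: both coefficients have "neutral priors in the log RR scale of" Normal(0, 0.35²), "which have a 95% prior" interval of 0.5 to 2.0 as risk ratios.
- Interaction: the coefficient β3 has a Normal(0, 0.14²) "prior which a priori gives a very small probability of 0.025" "of a qualitative interaction (meaning that the effect of longer cooling on the" outcome reverses according to whether deeper cooling is present. A reference is cited for this.
- Coding: "The binary variables depth and duration are coded as 1 for 32.0°C and 120" "hours (experimental interventions) and 0 otherwise; level of HIE is a" separate stratifying variable.
- Opening paragraph of the supplement: treatment effects get neutral priors with the 0.5 to 2.0 interval, and every other parameter gets a weakly informative prior, with conservative estimates as the aim.

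Section 5.1 assumes cell event rates of "AX=45%, AY=BX=30%, BY=25"%, which give margins of 37.5% and 27.5% with 726 infants. It says the trial assumes no large interaction and is not powered for one. Section 4.2 lists the absence of an interaction as the first secondary hypothesis.

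**The concern.** The probability that an effect changes sign depends on how large the effect is as well as on how large the interaction is. A main effect with prior SD 0.35 on the log scale often lies close to zero, where even a small interaction can reverse it. An interaction SD that is 40% of the main-effect SD should therefore give a reversal probability well above 0.025.

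The figure is the only reason the supplement gives for choosing 0.14. A reader uses it to judge how strongly the prior rules out reversal and how far a near-null posterior interaction reflects the data. If 0.025 is wrong as written, and the prior is also grouped with the weakly informative ones, the reader is misinformed on both counts for a quantity that the protocol names as a secondary hypothesis.

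**Working it through.** **Inputs.** From Supplement 2: β2 ~ Normal(0, 0.35²) for duration, β3 ~ Normal(0, 0.14²), 0/1 coding. From section 5.1: rates 0.45, 0.30, 0.30, 0.25 and N = 726, so 181.5 per cell. Independent priors and equal cells are assumed.

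**1. The neighbouring figures reproduce.** exp(±1.96 × 0.35) = 0.50 to 1.99 (stated 0.5 to 2.0). exp(±1.96) = 0.14 to 7.1 (stated 0.14 and 7). The difficulty is confined to the 0.025.

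**2. The stated event.** With 0/1 coding the duration effect is β2 at 33.5°C and β2 + β3 at 32.0°C. A change of direction means that these have opposite signs:

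P[β2(β2 + β3) < 0] = arctan(0.14/0.35)/π = arctan(0.4)/π = 0.121.

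A simulation of 4 million draws gave 0.121. By symmetry, benefit turning to harm alone has probability 0.061. To obtain 0.025 with main-effect SD 0.35, the interaction SD would have to be 0.35 × tan(0.025π) = 0.028.

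**3. Other readings.**

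| Reading | Probability |
|---|---|
| ±½ coding of the factors | 0.126 |
| Constraint "all $p_{ij} < 1$ in the model" applied to the prior | 0.133 to 0.135 |
| Both factors reverse at once (not the stated definition) | 0.022 |
| Fixed duration effect RR 0.667 (30% vs 45%) | 0.002 |
| Fixed duration effect RR 0.733 (27.5% vs 37.5%) | 0.013 |
| Fixed duration effect RR 0.76 | 0.025 |
| Fixed duration effect RR 0.80 | 0.055 |

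The last four rows are P(β3 > −log RR). The match at 0.76 is the 2.5% tail of the interaction prior itself: 1.96 × 0.14 = 0.274 and exp(−0.274) = 0.76. The protocol does not name 0.76 as a design effect.

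**4. How informative the interaction prior is.** Its 95% interval is exp(±0.274) = 0.76 to 1.32 as a ratio of risk ratios. The section 5.1 rates imply a ratio of (0.25 × 0.45)/(0.30 × 0.30) = 1.25, log 0.223.

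Sampling variance of the log ratio = Σ(1 − p)/(np) = (1.222 + 2.333 + 2.333 + 3.000)/181.5 = 0.0490, so SE = 0.221.

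Weight left to the data under this prior alone = 0.0196/(0.0196 + 0.0490) = 0.286. About 71% is removed, and the ratio falls from 1.25 to exp(0.286 × 0.223) = 1.07.

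**5. All stated priors together** (joint normal approximation, no encephalopathy level or centre term, N = 726).

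| Interaction prior SD | Posterior ratio of RRs | Share removed | Posterior SD of β3 |
|---|---|---|---|
| 0.14 | 1.04 | 83% | 0.12 |
| 0.35 | 1.09 | 60% | 0.18 |
| essentially flat | 1.13 | 46% | 0.21 |

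The last row shows that the intercept and main-effect priors by themselves account for 46%.

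**The case against.** The best defence of the 0.025 is that it is conditional. The supplement attaches it to the interaction prior and cites a reference that cannot be consulted here, and the prior does give exactly 0.025 for reversing an effect of RR 0.76. That derivation cannot be ruled out. But the sentence states no conditioning effect, and the protocol's own effects give 0.013 or 0.002. On this defence the sentence is incomplete rather than miscalculated, and it still has to change.

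The second defence is that the shrinkage is intended. The supplement says it wants conservative estimates, sections 4.2 and 5.1 do not expect a large interaction, and the prior is printed in full. This stands: a tight prior centred on no interaction is a legitimate choice and not an error. What remains is its description. An interval of 0.76 to 1.32 fits neither the 0.5 to 2.0 given for treatment effects nor the weakly informative label given to the rest.

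Three stronger inferences are tempting and are not supported:

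- A reader might blame the whole 83% on the interaction prior. It is the joint result of all the priors; the interaction prior alone removes about 71%.
- A reader might infer from the 0/1 coding that effects at 72 hours or at 33.5°C are passed off as marginal effects. The supplement does not say that the coefficients are reported as margins, and margins can be computed from the same posterior draws. The gap is also only about 0.01 (coefficient 0.735 against 0.749 averaged over the other factor on the log scale).
- A reader might infer that trial conclusions are at risk. The 0.025 enters no boundary, sample size or decision rule, and the marginal comparisons in section 5.2 use robust Poisson regression.

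**Conclusion.** The concern holds as a correction to how the prior is described. Under the priors and the definition that Supplement 2 itself gives, the probability of a qualitative interaction is about 0.12, nearly five times the stated 0.025. The stated value is right only as the chance of reversing a fixed RR of 0.76, which the text does not mention. The 0.12 assumes independent priors; the constraint that all probabilities stay below 1 moves it only to about 0.13.

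The interaction prior should also be called informative: at N = 726 it outweighs the data by about 2.5 to 1 (0.714 against 0.286) on the interaction that the design rates imply. That figure rests on equal cells and a normal approximation without encephalopathy level or centre. With 5% loss (N about 690) the prior alone removes 72%, and at N = 516 it removes 78%. The model specification, its fitted results and the frequentist analysis are untouched.

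**What to change.** 1. In Supplement 2, replace 0.025 by about 0.12, or keep 0.025 and state that it is the probability of reversing a fixed effect of RR 0.76.
2. In the opening paragraph of the supplement, exempt the interaction from the weakly informative label and give its 95% interval, 0.76 to 1.32.
3. Optionally, add one run with a wider interaction prior to show how far the posterior interaction depends on this choice. SD 0.35 is one possibility. It would still remove about 60% of the assumed interaction jointly with the other priors, and it carries a prior reversal probability of arctan(1)/π = 0.25, so it serves as a sensitivity check and not as a replacement.

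Items 1 and 2 are text edits. Item 3 costs one model run and a wider interval for the interaction (posterior SD about 0.18 against 0.12).
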